5.8.4 Parameters for drug non-compliance

Patients who are non-compliant with medication dosing, or who discontinue taking their medication, may remain in the study in observation. They will remain on their original follow-up schedule but will no longer be dispensed medication. It should be noted in WebEz that medication has stopped.

6. SELECTION OF STUDY PARTICIPANTS

Inclusion criteria

1. Males and females 18 years of age and older meeting 2009 RIS criteria¹
2. Identified RIS cases with the initial MRI demonstrating anomalies suggestive of demyelinating disease dated \geq 2009
3. Incidental anomalies identified on MRI of the brain or spinal cord with the primary reason for the acquired MRI resulting from an evaluation of a process other than MS
4. CNS white matter anomalies meeting the following MRI criteria:
 - a. Ovoid, well-circumscribed, and homogeneous foci with or without involvement of the corpus callosum

- b. T2-hyperintensities measuring > 3mm² and fulfilling 3 of 4 Barkhof-Tintoré criteria for dissemination in space
 - c. CNS anomalies not consistent with a vascular pattern
 - d. Qualitative determination that CNS anomalies have a characteristic appearance of demyelinating lesions
5. MRI anomalies do not account for clinically apparent neurological impairments in patients

Exclusion criteria

1. Women who are pregnant or nursing
2. Incomplete medical history or radiological data
3. History of remitting clinical symptoms consistent with multiple sclerosis lasting > 24 hours prior to CNS imaging revealing anomalies suggestive of MS
4. History of paroxysmal symptoms associated with MS (i.e. Lhermitte's or Uhthoff's phenomena)
5. CNS MRI anomalies are better accounted for by another disease process
6. The subject is unwilling or unable to comply with the requirements of the study protocol
7. Exposure to a disease modifying therapy for MS/RIS within the past 3 months
8. Exposure to high-dose glucocorticosteroid treatment within the past 30 days
9. Participation in other clinical trials involving treatment with a disease-modifying agent

8.1 Adverse Event Reporting

An adverse event is any untoward medical occurrence in a patient or clinical investigation subject administered a pharmaceutical product that occurs after first dose of study treatment through week 144 or EOS visit or early withdrawal/discontinuation visit, whether or not considered related to study treatment. Signs and symptoms existing prior to first dose and documented on the baseline Medical History form or Physical Examination Form are not considered AEs. Only baseline signs and symptoms that worsen while the subject is on the study drug are considered adverse events.

At every visit, participant will be questioned regarding the occurrence and nature of any adverse experiences. If any signs, symptoms or the results of the laboratory tests indicate an adverse effect, the study physician should determine the severity (grade) of the AE and judge the relationship to the study treatment according to the current version of the U.S. Department of Health and Human Services *Common Terminology Criteria for Adverse Events (CTCAE)*. In addition, if an adverse event necessitates medical care, appropriate care will be provided. Adverse events should be documented on the Adverse Event Report form, regardless of relationship to the study drugs. Notably, AEs thought to be due to treatment with the study drug are still reported as AEs in this study. The following information will be collected for all Adverse

Events:

- Start and stop dates
- Severity (See the Severity Grading section below)
- CTCAE score
- Relationship to study drugs (See the Association with the Study Drug below)
- Action taken with study drugs
- Treatment for the AE and outcomes

Severity Grading

For evaluation and reporting purposes, events will be graded by a numerical score according to their impact on the subject's ability to perform daily activities as follows:

- 1 - Mild (causing no limitation of usual activities)
- 2 - Moderate (causing some limitation of usual activities)
- 3 - Severe (causing inability to carry out usual activities)

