In the event that the absolute lymphocyte count is observed to be <500 cells/L during any time within the study, a repeat blood draw will be performed 3 months later. If a sustained reduction of the absolute lymphocyte count is observed (<500 cells/L), the study subject will be unblinded to the study medication and removed from the randomized portion of the trial. Repeat assessments will be performed monthly until the absolute lymphocyte count is >500 cells/L. Once the absolute lymphocyte count is found to be >500 cells/L, study subjects randomized to Tecfidera will be given the opportunity to receive Plegridy (covered by Biogen until study conclusion).

The rationale for providing these options to subjects was 2-fold: to conduct this placebo-controlled study ethically and to make every effort to continue to follow the subjects (for efficacy and safety evaluations), even after they discontinued the study treatment.

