8.3 Serious Adverse Event (SAE)

A serious adverse event means any adverse drug experience occurring at any dose that results in any of the following outcomes: death, a life-threatening adverse drug experience, requires participant hospitalization or prolongation of existing hospitalization, a persistent or significant disability/incapacity, or a congenital anomaly/birth defect. An important medical event that may not result in death, be life-threatening, or require hospitalization may be considered a SAE, when, based upon appropriate medical judgment, they may jeopardize the subject and may require medical / surgical intervention to prevent one of the outcomes listed above. Notably, any hospitalization, regardless of its nature, severity or etiology will be reported as an SAE. SAEs are collected from signing of Informed Consent through week 144 /or EOS visit or early withdrawal/discontinuation visit.

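### Section 8.1 defines adverse event severity twice and names the activity-limitation score for reporting, so symptom-free laboratory toxicity is labelled mild on that scale

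*Protocol*

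**What the plan says.** Protocol section 8.1 deals with severity in three places.

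- **Grading instruction.** The trigger covers laboratory findings: "If any signs, symptoms or the results of the laboratory tests indicate an adverse effect". In that case "the study physician should determine the severity (grade) of the AE and judge the relationship to the study treatment according to the current version" of CTCAE. Here severity and CTCAE grade are the same thing.
- **Items collected for every adverse event.** One item is "Severity (See the Severity Grading section below". The CTCAE score is listed separately, so each event carries two gradings.
- **Severity Grading paragraph.** "For evaluation and reporting purposes, events will be graded by a numerical score according to their impact on the subject's ability to perform daily activities". The bottom level reads "1 - Mild (causing no limitation of usual activities" and the top level "3 - Severe (causing inability to carry out usual activities". One moderate level lies between them.

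Two other sections bear on the point. Section 5.8.3 provides that after a sustained low lymphocyte count "the study subject will be unblinded to the study medication and removed from the randomized portion of the trial". Section 8.3 defines serious adverse events by outcomes that include "death, a life-threatening adverse drug experience, requires participant hospitalization or prolongation of existing hospitalization".

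**The concern.** One word, severity, has two definitions within one section, and the scale named for evaluation and reporting is the one that cannot register a laboratory abnormality unless the patient feels it. The trial looks for such abnormalities on a schedule: CBC and CMP are drawn at weeks 0, 12, 24, 48, 72, 96, 120 and 144. Low lymphocytes are also the one laboratory finding with its own rule for unblinding and removal from the randomized part of the trial.

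What is at stake is how the safety results read. Participants have no symptoms of MS by definition, so the tolerability and laboratory safety of the drug weigh heavily in any judgement of its value to them. If adverse events were reported by the scale that 8.1 names, an event that ended a patient's randomized treatment could appear as mild, and a reader could not tell from the severity level that an event had been life-threatening.

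**Working it through.** No arithmetic applies: no sample size, event count or error rate is involved, and the plan states no figure to reproduce. The check applies each scale, as written, to the same events.

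| Event | 1-3 activity score | CTCAE score | Captured elsewhere |
|---|---|---|---|
| Sustained low lymphocyte count, no symptoms | 1, mild, whatever the count | Recorded for the event | Count-based rule in 5.8.3; action taken with study drug (8.1) |
| Other laboratory abnormality, no symptoms | 1, mild, whatever its depth | Recorded for the event | Scheduled CBC and CMP results |
| Symptom that prevents usual activities | 3, severe | Recorded for the event | None needed |
| Life-threatening or fatal event | 3, severe, same level as the row above | Recorded for the event | Serious adverse event (8.3); outcome item (8.1) |

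1. **Laboratory events.** Level 1 is defined by absence of limitation. An abnormality that the patient does not notice causes none, so it meets that definition however far the value has moved. Levels 2 and 3 can be reached only through an effect on activities.
2. **Top of the scale.** Level 3 has no upper bound, so a life-threatening or fatal event fits there. It is not separated from an event that only stopped the patient's usual activities.
3. **Which scale governs.** The grading instruction ties severity to CTCAE. The item list and the Severity Grading paragraph tie it to the activity score. No sentence ranks them, but only the activity score is described as the one for evaluation and reporting.
4. **What is lost.** Nothing is lost from the database. The third column is filled for every event, and the fourth shows that the outcomes of most concern have a second route.

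Assumption: the protocol does not reproduce the CTCAE criteria, so no grade is given for any lymphocyte count. The argument needs only that CTCAE does not grade laboratory abnormalities solely by limitation of activities. The protocol's instruction to apply CTCAE to laboratory results suggests this but does not state it.

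**The case against.** The strongest reply is that two descriptors held in two fields are not a contradiction. CTCAE grades are collected for every adverse event, so laboratory toxicity by CTCAE grade can be tabulated from data the protocol already requires. Section 12 specifies no table of adverse event severity. The reporting phrase can be read as concerning the adverse event form rather than statistical summaries, and the choice of field to tabulate commonly belongs to the SAP, which is not shown.

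Much of this stands, and it rules out several stronger readings that a reader might infer:

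- *That the reported rate of severe laboratory toxicity must be zero.* This is true only on the activity score, and only for symptom-free events. The CTCAE score remains available.
- *That fatal or life-threatening events cannot be graded.* They fall in level 3 and are identified under 8.3. They lack a distinct level, and seriousness is in any case a separate attribute from severity.
- *That patients with low lymphocytes are less well protected.* The rule in 5.8.3 is triggered by the count and uses neither scale.
- *That referring to the current CTCAE version does harm.* The documents show no version change and no grade that would differ.

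The absence of a monitoring board (section 9) is a separate matter and does not enlarge this one.

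What the reply does not remove is that 8.1 itself names a scale for evaluation and reporting and gives sites two meanings for severity. That is a stated rule, not a detail left for later. A SAP could choose the CTCAE field, but it would then depart from the protocol's wording, and it would not change the instruction sites follow when completing the form.

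**Conclusion.** The point holds as a minor inconsistency in safety reporting. Section 8.1 assigns severity to CTCAE and also to a 1-3 activity score, names the activity score for evaluation and reporting, and does not say which prevails when they differ. Followed literally, symptom-free laboratory events are reported as mild whatever their depth, and life-threatening or fatal events are not distinguished from other severe ones on that scale.

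The documents allow no numerical size to be given. The affected class is laboratory adverse events without symptoms, plus the top category of the activity score. No data are lost, no patient-level action depends on the score, and the efficacy analyses are unaffected.

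The conclusion rests on two readings: that the activity levels are applied as worded, and that the reporting phrase extends to how adverse events are summarised. If it covers only the case form, what remains is the double use of the word severity.

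**What to change.** In 8.1, state that the CTCAE grade already collected is the severity used for evaluation and reporting, at the least for all laboratory adverse events. Keep the 1-3 score as a descriptive item and rename it 'activity impact' in the text and on the form, so that a 3 on one scale is not taken for a 3 on the other.

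The cost is a small change of wording and one field label. No assessment, data item or clinical rule changes. The one downside is that the severity table may look less favourable than it would on the activity score.

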8.2 Association with the Study Drug

Association with the use of the study drug means that there is a reasonable possibility that the adverse event may have been caused by the drug under investigation. All adverse events are graded with regard to their association with the use of the study drug. The classifications used include Not Related or Related.

8.3 Serious Adverse Event (SAE)

A serious adverse event means any adverse drug experience occurring at any dose that results in any of the following outcomes: death, a life-threatening adverse drug experience, requires participant hospitalization or prolongation of existing hospitalization, a persistent or significant disability/incapacity, or a congenital anomaly/birth defect. An important medical event that may not result in death, be life-threatening, or require hospitalization may be considered a SAE, when, based upon appropriate medical judgment, they may jeopardize the subject and may require medical / surgical intervention to prevent one of the outcomes listed above. Notably, any hospitalization, regardless of its nature, severity or etiology will be reported as an SAE. SAEs are collected from signing of Informed Consent through week 144 /or EOS visit or early withdrawal/discontinuation visit.

8.4 SAE Reporting Procedure

In the interest of subject safety and to fulfill regulatory requirements, all Serious Adverse Events, regardless of whether or not it is related to the study drug, should be reported to Quintiles Lifecycle Safety within 24 hours of event identification. Biogen or designee will forward a CIOMS form to the Sponsor-Principal Investigator to immediately onward submit to the FDA and all participating investigators in the study. All PIs are responsible for ensuring that all SAEs are recorded on the CRF and are reported to respective IRBs.

8.5 Withdrawal of Study Participants:

The researchers may decide to withdraw the patient from the study if:

- The medical problem becomes worse
- The researchers believe that participation in the research is no longer safe for the patient
- The researchers believe that other treatment may be more helpful
- The sponsor, IRB or the FDA stops the research for the safety of the participants
- The sponsor cancels the research
- The patient is unable to keep appointments or to follow the researcher's instructions

9. DATA SAFETY MONITORING BOARD (DSMB)

As Tecfidera is an approved FDA treatment for relapsing forms of multiple sclerosis, we do not anticipate any impediments to patient enrollment or significant adverse or serious adverse events. As a result, no data safety advisory board is required during the study.

10. INFORMED CONSENT

The informed consent form must be reviewed and approved by IRB. All revisions of the protocol must be reflected in the consent form and reviewed by the IRB. Obtaining informed consent is more than obtaining a signature on a form. It is a process designed to:

- Provide the participant with current and ongoing information about the study
- Ensure the participant understands the information that has been presented and has an opportunity to ask questions
- Discuss the participant's rights as outlined in the consent form
- Allow the participant the opportunity to agree or disagree to take part in the study, and
- Allow the participant the opportunity to freely withdraw from the study in the future. The investigator or coordinator should discuss in detail with the potentially eligible subjects about the nature, aims, duration, potential hazards of the study, and procedures to be performed during the study. The investigator or coordinator will explain all aspects of the study in lay language and answer all of the candidate's questions regarding the study. The investigator must also explain that the participants are completely free to refuse to enter the study or to withdraw from it at any time. The written informed consent form should be signed and personally dated and timed by the participant. Participants receive a copy of the informed consent form. The original copy of the signed and dated consent form should be kept in the participant's source document file and a copy should be scanned into the patient's medical record. Subjects who refuse to participate should be treated without prejudice.
- Should be obtained prior to any study-related procedures

11. DATA REVIEW AND DATABASE MANAGEMENT Clinical and radiographic information will be transmitted to Core Clinical Unit via secure FTP – MOVEit DMZ.

Quintiles will provide for support related to data management, safety management, and project management. Data should be entered into eCRF (Oracle Inform) within 7 days of the visit, except: Day 1 data, which should be entered within 24 hours.

Automatic validation programs will be implemented by the external vendor to assess for data discrepancies. At the end of the study, each participating PI will certify that the data entered are complete and accurate prior to database lock.

12. DATA ANALYSIS

The purpose of this study is to assess the risk for a first clinical neurological event related to CNS demyelination in a cohort of RIS subjects from the U.S.

12.1 Power calculation

A Bayesian approach has been used to calculate the sample size. The Bayesian approach is based on combining a prior distribution for the treatment effect with the result of the trial (which represents here the likelihood). The prior distribution for the effect of Tecfidera vs. placebo was built using the data from DEFINE and CONFIRM trials in RRMS.

12.1.1 Parameter estimates for the rate of events in the RIS cohort in a Bayesian framework

The parameters for the expected treatment effect of a 50% reduction in the risk of the first clinical event are $HR=0.50$ (i.e. $\log HR=-0.69$). A SD for $\log HR$ is set to 2.2 to get a power of 80% to detect a 50% reduction in the hazard of events with 80 patients per arm (original design). This base scenario is set in order to use the same assumptions done as for the original calculations.

Several scenarios were considered to allow a sensitivity analysis for the power calculations.

12.1.2 Parameters for the prior distribution – Scenario 1

The 2 arms treated with Tecfidera are pooled together (i.e. same efficacy)
Patients from DEFINE and CONFIRM are classified as “early RRMS” if they had:

- No previous treatment
- Less than 5 years from disease onset
- EDSS≤1.5

| | Placebo | Tecfidera | Total |
|-------|---------|-----------|-------|
| RRMS | 703 | 1372 | 2075 |
| Early | 68 | 157 | 225 |
| Total | 771 | 1529 | 2300 |

225 patients are classified as Early in the 2 trials merged.

Treatment effect in the “Early” group ($HR=0.24$, risk reduction=76%) $\log HR=-1.45$; $SE=0.31$.
Treatment effect in the rest of RRMS ($HR=0.59$, risk reduction 41%)

The parameters of the prior distribution, according to the Tecfidera effect in early RRMS in the DEFINE+CONFIRM studies, are: mean=-1.45, SD=0.31.

12.1.3 Parameters for the prior distribution – Scenario 2

The 2 arms treated with Tecfidera are pooled together (i.e. same efficacy)
We take the Tecfidera effect form the merged trials: $HR=0.58$, risk reduction=42%; $\log HR=-0.548$; $SE=0.073$.

The parameters of the prior distribution, according to the Tecfidera effect all the patients included in the DEFINE+CONFIRM studies, are: mean=-0.548, SD=0.073.

12.1.4 Parameters for the prior distribution – Scenario 3

The 2 arms treated with Tecfidera are pooled together (i.e. same efficacy)
We take the Tecfidera effect from the merged trials: HR=0.58, risk reduction=42%
We assume the treatment effect on the RIS cohort to be reduced by 20% since there is a portion of RIS that are not subclinical MS.

HR=0.58*1.20 =0.70

logHR=-0.36

mean=-0.36, SD=0.073.

12.1.5 Parameters for the prior distribution – Scenario 4

The 2 arms treated with Tecfidera are pooled together (i.e. same efficacy)
We take the Tecfidera effect from the merged trials: HR=0.58, risk reduction=42%; SE=0.073

We assume the treatment effect on the RIS cohort to be reduced by 30% since there is a portion of RIS that are not subclinical MS.

HR=0.58*1.30 =0.75; logHR=-0.282; mean=-0.282, SD=0.073

We report here the different power estimates for a sample size of 80 RIS patients (40 per arm) according to the 4 scenarios and 4 different assumptions on SD (representing those observed multiplied by 2, 3, 4 and 5).

| | Prior HR | Parameters for the prior | SD | | | |
|--|-----------------|----------------------------------|------|--------|--------|-----|
| | | | x2 | x3 | x4 | x5 |
| Scenario 1 (early RRMS, subgroup of the trials) | HR=0.235 | Prior mu=-1.45, SD=0.31 | 86% | 70% | 63% | 9% |
| Scenario 2 (all RRMS in the trials) | HR=0.58 | Prior mu= -0.548, SD=0.07 | 100% | 99.60% | 91.30% | 80% |
| Scenario 3 (all RRMS with an effect diluted by 20%) | HR=0.70 | Prior mu= -0.362, SD=0.07 | 99% | 86% | 70% | 61% |
| Scenario 4 (all RRMS with an effect diluted by 30%) | HR=0.75 | Prior mu= -0.282, SD=0.07 | 96% | 67% | 56% | 49% |

Overall, the power analysis shows that the projected sample size of 80 patients should result in adequate power for the majority of scenarios considered.

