- If subjects who were consented for 96 weeks choose not to extend their participation through week 114/or EOS, their week 96 should be recorded as 'early withdrawal' visit.

| Assessment | Week 108 | Week 120 | Week 132 | Week 144 | Relapse | Early Withdrawal | Unscheduled |
|---|----------|----------|----------|-----------|---------|------------------|-------------|
| Informed Consent | | | | | | | |
| Review of Eligibility | | | | | | | |
| Evaluation by Clinical Core and Central Imaging | | | | | | | |
| Randomization | | | | | | | |
| Record History and Demographics | | | | X | X | X | X |
| Visual Systems tests | | | | UTSW only | | UTSW only | |
| Patient Reported Surveys | | | | X | X | X | X |
| Physical Exam (including vital signs) | | | | X | X | X | X |
| Cognitive/Functional Assessments | | | | X | X | X | X |
| Pregnancy Test (urine) | | | | | | | |
| Blood draw : CBC/CMP for safety screening (local lab for PI review) | | X | | X | X | X | SOC |
| Biological sample for DNA/RNA: SERUM | | | | X | X | X | |
| CSF Samples (optional) | | | | X | | X | |
| Medication Assessment & Dispense rx via pt pick up or mail | X | X | X | X | | | |
| Brain MRI | | | | X | SOC | X | SOC |
| Cervical Spine MRI (optional – standard of care) | | | | SOC | | SOC | SOC |
| Telephone conversation | X | | X | | | | |
| Patient Compensation | | | | X | | | |
| Review adverse events & changes in medication | | | | | X | X | X |
| Collect remaining study medication | | | | X | | X | |

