13. TIMELINE ESTIMATE

- Contracting completion to IRB approval: 7 months
- Last patient in: September 30, 2019
- Last patient out: March 31, 2021
- Study completion and submission of final manuscript for publication: September 1, 2021

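### Section 12.1.1 states no event rate: its SD of 2.2 was back-solved from 80% power, reused at half the sample size, and hides an assumption of about 33 events in 80 patients

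*Protocol*

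**What the plan says.** The synopsis makes the primary analysis a Kaplan-Meier and log-rank comparison of time from randomization to first demyelinating event. Section 5.3 plans about 90 patients, 1:1, and refers to section 12 for the sample size justification.

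Section 12.1 describes a Bayesian calculation that combines a prior for the Tecfidera effect with the trial result. Section 12.1.1, whose heading names the rate of events, contains three things: a target HR of 0.50 (log HR −0.69); an SD for the log HR that "is set to 2.2 to get a power of 80% to detect a 50% reduction in the hazard of events" with 80 patients per arm under the original design; and the explanation "This base scenario is set in order to use the same assumptions done as for the original calculations". Neither this section nor any other gives a placebo event risk, an expected number of events or a dropout rate. The 16% (73/451) in section 2.2 is the share of a cohort prescribed therapy, not a conversion rate.

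Section 12.1.5 then tabulates power for 80 patients (40 per arm): four priors, for example "Prior mu= -0.548, SD=0.07" for Scenario 2, each with its SD multiplied by 2, 3, 4 and 5. It concludes that 80 patients give adequate power in most of the scenarios.

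On follow-up, section 5.3 gives 3 years or until March 31, 2021, with visits to week 144. Section 13 has "Last patient in: September 30, 2019". A footnote to the table in section 5.6 deals with an extension: "If subjects who were consented for 96 weeks choose not to extend their participation".

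**The concern.** In a log-rank or Cox comparison the precision of the log HR is governed by the number of events; with 1:1 allocation its variance is about 4/events. A per-patient SD is therefore an event rate in disguise. Here that SD was not derived from a rate. It was solved from the power that was wanted, so in the base case power is the input and the SD the output. The value was then carried into a design with half the patients per arm.

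What is at stake is whether the table shows what it is used to show. It has 16 cells, but all share one unstated event yield, and the sensitivity analysis moves only the prior. A reader cannot tell how many events the trial must observe, cannot judge whether the planned follow-up can deliver them, and cannot see how much of the claimed power comes from the earlier trials and how much from this one.

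**Working it through.** **Inputs from the protocol.** HR 0.50 (log HR −0.69), SD 2.2, 80% power at 80 per arm (12.1.1); 40 per arm and the four priors (12.1.5); about 90 patients, 1:1 (5.3); last patient in September 30, 2019 and last out March 31, 2021 (13); week 144 as the last scheduled visit (5.3). **Assumed:** two-sided 0.05, proportional hazards, no dropout.

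**1. Reproduce the stated 80%.** With SE = 2.2/√80 = 0.246, power = Φ(0.69/0.246 − 1.96) = 80.1% (80.5% with ln 2). Solving backwards, √80 × 0.69/(1.96 + 0.84) = 2.20. Other readings fail: 2.2·√(2/80) gives 51%, 2.2/√160 gives 98%, and one-sided 0.05 gives 88%. So SE = 2.2/√(n per arm).

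**2. Show that the current table uses the same 2.2.** At 40 per arm, SE = 2.2/√40 = 0.348. Take a normal prior (mean μ, SD s), V = 1/(1/s² + 1/SE²), w = V/SE², true HR 0.50, and success when the posterior mean is below −1.96√V. Then

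power = Φ{[−1.96√V − (−0.693w + (1−w)μ)]/(w·SE)}.

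Example, Scenario 4 ×3: s = 0.21, V = 0.0323, w = 0.267, and the result is 66% (printed 67%). In all, 14 of 16 cells agree within 2 points. The exceptions are Scenario 1 ×5 (printed 9%, computed 58%) and Scenario 4 ×5 (49% against 51%).

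**3. Convert the SD to events.** From SE = 2/√D, D = 4n/2.2² = 0.826n: 66 events in 160 patients, 33 in 80, or 41% of all randomized. With placebo risk p and HR 0.50, the Tecfidera risk is 1 − √(1−p). Solving [p + 1 − √(1−p)]/2 = 0.413 gives p = 52% and 31% on Tecfidera. Freedman's formula (71 events in 160), or 1/p₁ + 1/p₂ = 2.2², gives 55% and 33%.

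**4. Log-rank power, no prior, HR 0.50.** Power = Φ(0.693·√D/2 − 1.96), with D = n[p + 1 − √(1−p)]. Risks below 52% are assumed values, since the protocol gives none.

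| Placebo risk | Events, 40/arm | Power, 40/arm | Power, 45/arm |
|---|---|---|---|
| 52% (implied) | 33 | 51% | 56% |
| 40% | 25 | 41% | 45% |
| 30% | 19 | 32% | 35% |
| 20% | 12 | 23% | 25% |

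**5. The Bayesian table at an assumed 30% placebo risk.** D = 40 × (0.30 + 0.163) = 18.5, so SE = 2/√18.5 = 0.465.

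| Prior SD ×2/×3/×4/×5 | Printed (%) | At 30% placebo risk (%) |
|---|---|---|
| Scenario 1 | 86/70/63/9 | 79/53/44/39 |
| Scenario 2 | 100/99.6/91.3/80 | 100/99/83/62 |
| Scenario 3 | 99/86/70/61 | 100/71/44/35 |
| Scenario 4 | 96/67/56/49 | 92/38/26/24 |

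The Scenario 1 ×5 figure should be compared with the computed 58%, not the printed 9%. Cells at 80% or more go from 8 of 16 to 5 of 16. Scenario 2 ×2 and ×3 and Scenario 3 ×2 stay at 99–100% even at a 20% placebo risk, because the prior decides them.

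**6. Follow-up.** September 30, 2019 to March 31, 2021 is 548 days, or 78 weeks, the planned minimum; the schedule ends at week 144. A 52% risk over 144 weeks is 1 − 0.48^(52.18/144) = 23% per year. Shorter follow-up would require a higher annual risk.

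**The case against.** The stated arithmetic is sound: 2.2 does return 80%. The protocol openly says that it keeps the original assumptions, and those may have rested on an explicit event rate that is not shown. The table powers are genuine results given that base. This stands. The defect is a missing and untested assumption, not a miscalculation.

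Four stronger readings are tempting, and the documents do not support them.

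- **That 52% is too high, so the trial is underpowered.** The protocol contains no conversion rate for RIS, so it cannot be used to call 52% high, low or right. The lower risks above are illustrations.
- **That every cell depends on the hidden rate.** Three cells are settled by the prior and barely move. Scenario 4 loses heavily, but Scenario 2 much less, so all four rows must be read together.
- **That the missing event rate takes power from 80% to 51%.** At the implied 33 events, that drop comes from halving the sample and leaving out the prior. The 51% is still relevant, because the log-rank test named as primary uses no prior.
- **That the SD was built on 52% converting within 78 to 144 weeks.** It was set for the original design, whose follow-up is not stated. The window belongs to the current design and applies only because 2.2 was reused. Nor should one annualize over 78 weeks for everybody, as that is the minimum, for the last patient in.

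**Conclusion.** The concern holds as a back-solved and undisclosed assumption. The power table rests on about 33 events in 80 patients, or about 52–55% on placebo and 31–33% on Tecfidera, which the protocol neither states, defends nor varies. With that yield the primary log-rank test has about 51% power at 40 per arm and 56% at 45. The closing statement of adequate power is therefore not shown for the primary test; it depends on the prior and on the hidden event count.

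These figures assume two-sided 0.05, proportional hazards and no dropout; dropout would raise the underlying risk needed. The range 52–55% reflects the choice of approximation. The true HR of 0.50 behind the table, and its success rule, are inferred from the fact that they reproduce 14 of 16 cells.

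**What to change.** In section 12.1.1, replace the back-solved SD with a stated placebo event risk, and its source, over the planned follow-up (78 weeks for the last patient in, up to 144). Derive SE = 2/√(expected events) and state alpha and sidedness. Disclose that the current table assumes about 33 events in 80 patients.

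In section 12.1.5, restate all four scenario rows, and add the log-rank power without the prior, over a range of placebo risks such as 20–52%. Reword the closing sentence on adequate power to match. Comparing the assumed count with blinded pooled events is a useful but optional addition.

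The cost is a recalculation and protocol wording. The stated power will look less favourable. No patients are added, and the endpoint and primary test are unchanged.
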